11.3 Exploratory Endpoints Analysis

• Demonstration of NB-IS TCD accuracy to Spencer Logarithmic Scale (SLS) Grade and International Consensus Criteria (ICC) grade for diagnostic accuracy.

DWF-C0001-001 CONFIDENTIAL Page 36 of 44

11.4 Imaging Core Lab Analysis

All de-identified imaging data will be sent to a core laboratory which will provide independent quantitative and qualitative assessment of all NB-IS TCD and SOC TCD, TTE, and TEE bubble study data. They will be blinded to the study and local diagnostic report data and provide independent review. The Core Lab interpretations will supersede all local interpretations and will be applied to all study endpoint analyses as applicable.

11.5 RLS/PFO Validation and Analysis

Evaluation of correlation between diagnostic imaging standard of care (SOC TCD/TTE/TEE) and NB-IS TCD diagnostic performance by an independent core laboratory. Success criteria will include clinical validation of NB-IS TCD for RLS/PFO detection targeting (i) 40% increase in NB-IS TCD sensitivity compared to TTE sensitivity and (ii) NB-IS TCD sensitivity ≥ 90% compared to SOC TCD sensitivity.

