5.3 Study Entry Criteria – TTE Main Study

5.3.1 Inclusion Criteria

A subject must meet all of the following inclusions criteria to be enrolled in the study:

- 1. Subject 18 years of age and older.
- 2. Subject presents with a clinical condition characterized by neurological signs and symptoms that, in the opinion of the investigator, include embolic stroke or TIA in the differential diagnosis.
- 3. Scheduled for a transthoracic echocardiograph (TTE) study with agitated saline contrast (bubble study) within ±30 days of informed consent.
- 4. Subject is able to successfully perform a Valsalva Maneuver (VM).
- 5. Subject or Legally Authorized Representative has the ability to provide informed consent and comply with the protocol.

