6.5 Study Schedule

6.5.1 Schedule of Assessments

Schedule of Assessments					
Assessments	Screening ¹	Procedure ¹	Follow-Up ¹		
Informed Consent	х				
Demographics	Х				
Relevant Medical History	Х				
Physical Exam ◆	Х				
SOC TCD Bubble Study Exam ◆		O ⁴			
NB-IS TCD Bubble Study Exam		X ²			
Transthoracic Echocardiograph (TTE) Bubble Study ◆		X ³			
Transesophageal Echocardiograph (TEE) ◆		O ⁴ / X ⁸			
PFO Closure Decision ◆			X ⁵		
Classification of Potential Causative Mechanism in PFO–Associated Stroke ⁷ ♦			Х		
PFO Closure Procedure ◆			O _e		
Device-Related Adverse Events		Х			
Procedure-Related Adverse Events		х			
Concomitant Medications	х	х			
Device Deficiencies		Х			

- ♦ Standard of Care X = Required O = Optional, if performed
- 1. Screening, Procedure, and Follow-Up Visits can occur on the same day
- 2. NB-IS TCD performed with contrast agent of 9 ml bacteriostatic saline with 1 ml air mixed 10 times. Performed at Rest AND with VM 60 sec recordings each in supine positions AND with HOB raised to 45 degrees.
- 3. TTE can be performed within ±30 days of informed consent per SOC.
- 4. SOC TCD and TEE results collected if performed as applicable per standard of care.
- 5. PFO closure decision collected post diagnostic imaging procedures.
- 6. PFO closure procedure data collected within 60 days post diagnostic workup, if performed
- 8. SOC TTE or TEE will be required after the first 150 TTE subjects are enrolled and can be performed within ±30 days of informed consent per SOC.

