6.12.3 SOC Transcranial Doppler Ultrasound Procedure (TCD) (as applicable)

If SOC TCD bubble study is performed during subject participation in the study, preference is for this exam to be conducted in same session as the NB-IS TCD with the same individual administering the bubble injections with the SOC TCD bubble exam occurring before NB-IS TCD. The SOC TCD bubble study will be performed per standard of care, however, if possible, preference would be to collect measurements similar to NB-IS TCD exam (e.g., supine position at Rest and with VM, 45 degrees at Rest and with VM, etc.).

The following data points will be collected for the SOC TCD procedure:

- SOC transcranial Doppler Ultrasound (TCD) bubble study local results (SOC)
 - Date/time of SOC TCD bubble study
 - SOC TCD scan Start/Stop times with and without VM (as applicable)
 - Saline/Air Injection(s) Start/Stop time(s) with and without VM (as applicable)
 - Head inclination (degree)/subject positioning/location of the exam
 - Local Positive/Negative results for RLS/PFO
 - Local Spencer Logarithmic Scale (SLS) grade (with and without VM)
 - Local International Consensus Criteria (ICC) grade (with and without VM)

•

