11.2 Secondary Technical Efficacy Endpoint(s) Analysis

- % detection of false positives (FP), comparison of NB-IS TCD with TTE
- % detection of true negatives (TN) (specificity), comparison of NB-IS TCD with TTE
- % detection of false negatives (FN), comparison of NB-IS TCD with TTE
- Positive Predictive Value (PPV), comparison of NB-IS TCD with TTE
- Negative Predictive Value (NPV), comparison of NB-IS TCD with TTE
- Demonstration of NB-IS TCD diagnostic performance to SOC TCD for diagnostic accuracy parameters (sensitivity, specificity, PPV, NPV).
 - o If bilateral signals are found, the microbubble count will be sum across both vessels.
 - o If only a unilateral signal is found, the microbubble count will be doubled for the total count.
 - Spencer Logarithmic Scale (SLS) and International Consensus Criteria (ICC) gradings from the Imaging Core Lab for NB-IS TCD and SOC TCD will be compared for analysis.
- Demonstration of NB-IS TCD diagnostic performance targeting to transesophageal echocardiography (TEE) for diagnostic accuracy parameters (sensitivity, specificity, PPV, NPV).
- % detection of intervenable shunts, comparison of NB-IS TCD with TTE
 - For NB-IS TCD, Grade 3 and above (>30 microbubbles) on the Spencer Logarithmic Scale (SLS) and International Consensus Criteria (ICC) considered intervenable shunt¹⁰.
 - o For TTE, >20 microbubbles per 2016 American Society of Echocardiography Guidelines and Standards²³ considered intervenable shunt.
- NB-IS TCD No Window rate performance to SOC TCD parameters (including both unilateral and bilateral absent acoustic windows).
- % success rate of NB-IS TCD
 - o Incidence of failed registrations (device unable to register)
 - Incidence of bilateral signals not found (no evaluable signals found both sides)
 - Incidence of unilateral signals not found (evaluable signal found on one side)
 - An adequate, evaluable, and complete study is defined for the purposes of this protocol as successful acquisition of a unilateral signal at 40-65mm depth range recorded for the duration of the bubble study in the Resting position and with Valsalva Maneuver.
- Incidence of device malfunctions

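### Success criterion (ii) and the no-window comparison depend on an optional SOC TCD exam with no minimum number, decision rule or failed-window record, so either may rest on few or incomplete data.

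*Combined protocol and SAP*

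**What the plan says.** Section 11.5 and the Data Analysis part of the synopsis set two success criteria, joined by an and: "i) 40% increase in NB-IS TCD sensitivity compared to TTE sensitivity" and "ii) NB-IS TCD sensitivity ≥ 90% compared to SOC TCD sensitivity". Sections 4.2 and 11.2 also list NB-IS TCD versus SOC TCD among the secondary technical endpoints.

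The schedule in 6.5.1 marks the SOC TCD exam O, under the key "X = Required O = Optional, if performed". Its note 4 reads "SOC TCD and TEE results collected if performed as applicable per standard of care". Section 6.12.3 opens conditionally: "If SOC TCD bubble study is performed during subject participation in the study". The main-study imaging entry criterion (5.3.1) is "Scheduled for a transthoracic echocardiograph (TTE) study with agitated saline contrast (bubble study) within ±30 days of informed consent". Section 5.4.1 accepts TTE or TEE. Neither asks for SOC TCD.

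Section 11.2 also plans the comparison "NB-IS TCD No Window rate performance to SOC TCD parameters (including both unilateral and bilateral absent acoustic windows". The SOC TCD items in 6.12.3 are date, scan and injection times, position, "Local Positive/Negative results for RLS/PFO", and the SLS and ICC grades. Section 6.3 removes all clinical and imaging data of a subject whose NB-IS scan is inadequate from the final analysis.

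**The concern.** A named success criterion of a pivotal study should have data behind it by design. Criterion (i) does: TTE is required in the main study and the comparison is powered. Criterion (ii) has whatever routine care supplies. The plan gives it no minimum number of exams, no sample size, and no statement of whether 90% is a point estimate or a confidence limit. The study could meet (i) and be unable to say anything about (ii). It could also pass or fail (ii) on so few pairs that the result says little about the device.

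The no-window comparison has a related gap. It needs failures counted the same way on both sides. For SOC TCD there is no listed place to record an absent window or an abandoned attempt. For NB-IS, 6.3 takes failed scans out of the analysis.

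**Working it through.** **1. The plan's own figures (section 11.6).** Inputs: sensitivities 0.90 and 0.50, discordant proportion 0.50, prevalence 0.30, two-sided McNemar test at 0.05. With N = 100 there are 0.30 × 100 = 30 diseased pairs. Discordant pairs follow Bin(30, 0.50), and the share favouring TCD is 0.45/0.50 = 0.90. Exact power is 0.89995, as stated. For TEE, 147 × 0.30 = 44.1 positives at 90% give a Clopper–Pearson width of 0.198 against the stated 20%. Both reproduce and neither is in dispute. There is no corresponding figure for SOC TCD.

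**2. Pairs available for criterion (ii).** Uptake is an assumption, because the documents give none. About 30% of those examined are taken as SOC TCD positive. Pairs = subjects × uptake × 0.30.

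| Uptake | 150 subjects | 300 subjects |
|---|---|---|
| 10% | 15 exams, 4.5 positive | 30 exams, 9 positive |
| 20% | 30 exams, 9 positive | 60 exams, 18 positive |
| 50% | 75 exams, 22.5 positive | 150 exams, 45 positive |

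At zero uptake there is no estimate.

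**3. Chance of an observed value of at least 90%.** Here (ii) is read as a point estimate among SOC-positive subjects. With n pairs and k = 0.9n rounded up, P = Σ C(n,x) pˣ(1−p)ⁿ⁻ˣ for x from k to n.

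| n | Needed | True 90% | True 95% |
|---|---|---|---|
| 4 | 4/4 | 0.9⁴ = 66% | 0.95⁴ = 81% |
| 9 | 9/9 | 0.9⁹ = 39% | 0.95⁹ = 63% |
| 18 | 17/18 | 45% | 77% |
| 22 | 20/22 | 62% | 91% |
| 45 | 41/45 | 53% | 93% |

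With 4 pairs, a device with true sensitivity 85% passes with probability 0.85⁴ = 52%.

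**4. Precision.** When all n pairs agree, the exact 95% lower limit is 0.025^(1/n). For 9/9 this is 0.025^(1/9) = 0.664. At an observed 90%, the Clopper–Pearson interval is 77.3–96.9% (20 points) with 45 pairs, 70.0–98.5% (29 points) with 22.5, and 34–100% (66 points) with 4.5. With 9 pairs the width is 47 points.

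If 90% were meant as a lower confidence limit, 0.025^(1/n) ≥ 0.90 first holds at n = 36. That is 36 pairs, all concordant, or 36/0.30 = 120 SOC TCD exams.

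**5. No-window comparison, section against section.**
- Section 11.2 itemises failed registrations and signals not found on one or both sides for NB-IS, and compares no-window rates with SOC TCD.
- Section 6.12.3 lists no SOC TCD item for an absent window or an abandoned attempt, and results are taken only when the exam is performed. SOC failures may go unrecorded, which would lower the SOC rate.
- Section 6.3 calls a scan adequate when at least a one-sided signal is held through the bubble study, and excludes all data otherwise. Taken literally, bilateral NB-IS failures leave the analysis while one-sided ones stay, which lowers the NB-IS rate.

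Both rates can be understated, so the direction of bias in their difference cannot be fixed from the documents.

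**The case against.** The best case against the point is that scarcity is assumed. The study may enrol up to 300 subjects and collects SOC TCD in both parts. Section 11.6 puts prevalence at no less than 30%. With 45 pairs, a device with true sensitivity 95% meets a point-estimate rule 93% of the time. The documents also expect some SOC TCD: section 6.9 lists it with standard practice (if performed), 6.12 and 6.12.3 set blinding and session order for it, and the synopsis plans a single-site exploratory sub-study using standard TCD. This stands as a reason not to predict that data will be absent. A reader might infer that (ii) will have no data, or that only a few TCD-equipped sites will contribute. The documents give neither uptake nor site capability, so neither inference is supported. Equally, none of these passages secures a number, and section 2.4 itself describes TCD as too little used.

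On windows, a reader might infer that abandoned SOC attempts are certainly lost and the SOC rate is forced to zero. That goes too far. The eCRF is not among the documents. The NB-IS list in 6.12.4 lacks window fields too, although 11.2 reports them. Section 11.4 sends SOC TCD imaging to the core laboratory, and conditional collection does not say how an abandoned attempt is classed. What remains is that capture is unspecified: an attempt stopped before injection may leave no bubble study to review.

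Finally, NB-IS versus SOC TCD is already a secondary endpoint, and a required minimum of SOC TCD exams would also resolve criterion (ii). Both are true. The conflict lies in the success wording of 11.5 and the synopsis.

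**Conclusion.** The point holds as a risk that the plan leaves open. Criterion (ii) depends on an optional exam with no minimum number and no decision rule. Under assumed uptake of 10% to 50%, it would rest on about 4–5 to 22 SOC-positive pairs among 150 subjects, or 9 to 45 among 300. At the low end the result is close to uninformative. At the high end a point-estimate rule is workable for a device with true sensitivity 95%, but the interval at an observed 90% is still about 20 points wide. These figures rest on the plan's 30% prevalence, the assumed uptake, and the point-estimate reading of (ii).

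The no-window comparison is unsupported as written. SOC failures may go unrecorded and NB-IS failures are excluded under 6.3, with unknown net direction.

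This should be fixed, but it does not threaten the main result: the primary TTE comparison and its power are unaffected.

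**What to change.** - **11.5 and synopsis:** rest the success decision on criterion (i). Keep NB-IS versus SOC TCD as the secondary endpoint it already is in 4.2 and 11.2, reported as positive and negative agreement with exact 95% confidence intervals, the number of pairs and the contributing sites.
- **6.12.3 and eCRF:** add whether SOC TCD was attempted (yes/no) and whether a window was found on the right and on the left, completed also for abandoned attempts. Record the same for NB-IS in 6.12.4.
- **11.2:** compute the no-window comparison in all subjects attempted with both methods.
- **6.3:** state that the exclusion of inadequate NB-IS scans does not apply to the no-window and success-rate endpoints.

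The cost is protocol wording and a few eCRF fields, with no added exam. The sponsor gives up a formal success claim against SOC TCD. If that claim matters, the alternative is to keep (ii) with a prespecified minimum number of SOC-positive pairs and a stated decision rule, which means securing the SOC TCD exams to supply them.

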2.3 Limitations

Although TTE is the most frequently used non-invasive technique for the assessment of RLS, it is limited by its dependence on the expertise of the technician performing the exam. Furthermore, its moderate sensitivity (45.1%) but high specificity (99.6%) in RLS indication should not be relied upon in the determination of treatment for ESUS patients⁶.

While TEE is considered the gold standard for visualization of the PFO after its presence has been indicated, its invasive nature can make it difficult for the patient to comply with the necessary steps for the VM. Although TEE is contraindicated in patients with dysphagia or esophageal issues, its sensitivity and specificity are 95% and 95% for indication of RLS⁷.

Like TTE, the diagnostic value of TCD is limited by the expertise of the technician performing the exam and the presence of optimal acoustic windows. Signal acquisition is a well-documented obstacle in TCD evaluation regardless of pathology and is no different in the case of RLS

DWF-C0001-001 CONFIDENTIAL Page 14 of 44

assessment⁸. However, unlike TTE, TCD has shown excellent sensitivity and specificity in RLS detection (96.1% and 92.4%, respectively) against the gold standard of TEE⁶.

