4.1 Primary Efficacy Endpoint

 % detection of RLS/PFO with NB-IS TCD compared against standard of care Transthoracic Echocardiography (TTE)

4.2 Secondary Technical Efficacy Endpoints:

- % agreement for detection of RLS/PFO with NB-IS TCD vs SOC TCD
- % agreement for detection of RLS/PFO with NB-IS TCD vs Transesophageal Echocardiography (TEE)
- % agreement for detection of clinically significant shunts with NB-IS TCD vs TTE
- No window rate (including both unilateral and bilateral absent acoustic windows)
- Success rate of the NB-IS TCD
- Incidence of NB-IS device malfunctions

4.3 Exploratory Endpoints:

 Development of an automated algorithm for Spencer Logarithmic Scale¹⁰ and International Consensus Criteria grading of RLS¹¹

4.4 Primary Safety Endpoint:

Incidence of device-related serious adverse events.

4.5 Secondary Safety Endpoints:

Incidence of procedure-related adverse events related to agitated saline injection before and after VM (headache, allergic reactions, new onset neurological deficit, ischemic stroke, TIA or

DWF-C0001-001 CONFIDENTIAL Page 18 of 44

pulmonary embolism complicating agitated saline contrast injection, etc) will be closely monitored and prospectively collected¹².

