11.6 Sample Size Calculation

The present study was powered based on the results of a recent meta-analysis reporting a pooled TCD sensitivity of 96.1% for RLS detection, while the pooled TTE sensitivity was estimated at 45.1% (absolute difference of 51%)⁶. For power calculations, we used a more moderate effect size of 40% increase in the sensitivity of NB-IS TCD compared to TTE.

A sample size of 100 subjects achieves 90% power to detect a difference of 40% between two diagnostic tests whose sensitivities are 90% (TCD) and 50% (TTE). This procedure uses a two-sided McNemar test with a significance level of 0.05. The mean prevalence of PFO in the population of patients with cryptogenic stroke is at least 30%². The proportion of discordant pairs has been set at 0.500.

[figure not shown]
		Sensitivity	ity Sensitivity Proportion					
		of Test 1	of Test 2		Discordant	Prevalence		
Power	N	Se1	Se2	Se1-Se2	D	Р	Alpha	Beta
0.00000	10	0.900	0.500	0.400	0.500	0.300	0.05000	
	1.00000							
0.00830	20	0.900	0.500	0.400	0.500	0.300	0.05000	
	0.99170							
0.12990	30	0.900	0.500	0.400	0.500	0.300	0.05000	
	0.87010							
0.32013	40	0.900	0.500	0.400	0.500	0.300	0.05000	
	0.67987							
0.49003	50	0.900	0.500	0.400	0.500	0.300	0.05000	
	0.50997							
0.62345	60	0.900	0.500	0.400	0.500	0.300	0.05000	
	0.37655							
0.72404	70	0.900	0.500	0.400	0.500	0.300	0.05000	
	0.27596							
0.79937	80	0.900	0.500	0.400	0.500	0.300	0.05000	
	0.20063							
0.85654	90	0.900	0.500	0.400	0.500	0.300	0.05000	
	0.14346							
0.89995	100	0.900	0.500	0.400	0.500	0.300	0.05000	
	0.10005							
0.93182	110	0.900	0.500	0.400	0.500	0.300	0.05000	

DWF-C0001-001 CONFIDENTIAL Page 37 of 44

Protocol ID: NA-07BBL-01 Version Date: August 2, 2021

	0.06818						
0.95405	120	0.900	0.500	0.400	0.500	0.300	0.05000
	0.04595						
0.96898	130	0.900	0.500	0.400	0.500	0.300	0.05000
	0.03102						
0.97890	140	0.900	0.500	0.400	0.500	0.300	0.05000
	0.02110						
0.98561	150	0.900	0.500	0.400	0.500	0.300	0.05000
	0.01439						

 $\label{eq:vsN} vs~N$ Se1=0.900 Se2=0.500 D=0.500 α =0.050 P=0.300 2-Sided McNemars Test

Given previous reports indicating a prevalence of suboptimal transtemporal windows in 5% of Hispanic²⁰, 5% of Caucasian²¹, 9% in African American¹⁹ and 14% of Asian²² individuals aged <60 years, we increased our projected sample size by 20% (n=120). In addition, the final sample size

DWF-C0001-001 CONFIDENTIAL Page 38 of 44

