was further increased by 20% (n=144) in order to account for an anticipated dropout rate of 20%. Consequently, the final study sample was set at 144 individuals.

The sensitivity of TCD against TEE for right-to-left shunt detection has been estimated 90% in a recent meta-analysis²⁴. A sample size of 147 patients produces a two-sided 95%CI with a 95%CI width equal to 20% when the sample sensitivity is 90% and the prevalence is 30%. After the first 150 TTE subjects in the Main study are enrolled, the study will continue to enroll up to an additional 150 subjects that received a TTE or TEE bubble study.

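### Success criterion (ii) names no reference standard; read with section 11.2 it scores NB-IS against an imperfect SOC TCD, which measures agreement and not sensitivity for shunt

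*Combined protocol and SAP*

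**What the plan says.** Section 11.5, repeated under Data Analysis in the synopsis, gives two success criteria. The first is "40% increase in NB-IS TCD sensitivity compared to TTE sensitivity". The second is "NB-IS TCD sensitivity ≥ 90% compared to SOC TCD sensitivity". Neither names a reference standard.

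The only analysis specified for the SOC TCD comparison is in section 11.2: "Demonstration of NB-IS TCD diagnostic performance to SOC TCD for diagnostic accuracy parameters (sensitivity, specificity, PPV, NPV"). The same list uses a parallel construction for TEE. Section 4.2 describes the endpoint differently, as percent "agreement for detection of RLS/PFO with NB-IS TCD vs SOC TCD".

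On the accuracy of TCD, section 2.3 says that "TCD has shown excellent sensitivity and specificity in RLS detection (96.1% and 92.4%, respectively) against the gold standard of TEE". On prevalence, section 11.6 says that "The mean prevalence of PFO in the population of patients with cryptogenic stroke is at least 30"%, and it uses 30% for sizing. Note 4 to the schedule of assessments says that SOC TCD and TEE results are collected only where those exams are done as standard of care.

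**The concern.** Sensitivity needs a standard that says who truly has a shunt. If SOC TCD fills that role, every SOC TCD false positive counts as a shunt that NB-IS ought to find. A device that correctly calls such a subject negative is charged with a miss. A device that repeats the error is credited with a detection.

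This is one of only two stated success criteria. If its meaning is open when the data are read, the reference could be chosen afterwards. Under the section 11.2 reading, neither a pass nor a fail would tell us whether robotic TCD finds shunts as well as manual TCD does.

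**Working it through.** **The plan's own figures.** No sample size or power is stated for criterion (ii). The two figures that are stated reproduce:

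- The exact two-sided McNemar power with 30 shunt-positive subjects (100 × 0.30), sensitivities 0.90 and 0.50 and discordant proportion 0.50 is 0.89995, as tabulated in section 11.6.
- The TEE precision statement (147 subjects, about 44 with shunt, sensitivity 90%) gives a Clopper-Pearson 95% CI width of 0.198, consistent with the stated 20%.

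**Inputs.** TCD sensitivity Se = 0.961 and specificity Sp = 0.924 against TEE (section 2.3). Prevalence p = 0.30 (section 11.6). As a range I assume 25% to 43%. Section 2.1 gives 25% as the general-population figure. Its 43% is a share of cryptogenic strokes attributed to shunt, not clearly a prevalence, and serves only as an assumed upper point.

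**Step 1: a device that agrees perfectly with TEE.** Scored against SOC TCD, its expected sensitivity is the PPV of SOC TCD. No assumption about correlated errors is needed, because such a device makes none.

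PPV = Se·p / [Se·p + (1 − Sp)(1 − p)]

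| p | Se·p | (1 − Sp)(1 − p) | Expected score |
|---|---|---|---|
| 25% | 0.2403 | 0.0570 | 80.8% |
| 30% | 0.2883 | 0.0532 | 84.4% |
| 35% | 0.3364 | 0.0494 | 87.2% |
| 40% | 0.3844 | 0.0456 | 89.4% |
| 43% | 0.4132 | 0.0433 | 90.5% |

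The score reaches 90% when p/(1 − p) = 9 × 0.076/0.961 = 0.712, that is p = 41.6%. With section 11.6's alternative TCD sensitivity of 90%, the 30% row becomes 0.27/0.3232 = 83.5%.

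As an illustration, suppose all 150 main-study subjects had SOC TCD. About 150 × 0.3415 = 51 would be SOC TCD positive, and the device would need 46 of 51. The binomial probability of that at 84.4% is about 17%.

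**Step 2: a device with the same accuracy as SOC TCD.** Let r be the error correlation between the two exams, given true status, and take p = 0.30.

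- Both positive, shunt present: 0.961² + r × 0.961 × 0.039
- Both positive, shunt absent: 0.076² + r × 0.076 × 0.924
- Score = [0.30 × first + 0.70 × second] / 0.3415

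r = 0 gives (0.2771 + 0.0040)/0.3415 = 82.3%. r = 0.5 gives (0.2827 + 0.0286)/0.3415 = 91.2%. r = 1 gives 100%.

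**Step 3: what 90% demands.** The score is 0.844·a + 0.156·f, where a is the share of SOC TCD true positives that NB-IS also calls positive and f is the share of SOC TCD false positives that it repeats. Setting this to 0.90 gives f = 36% when a = 1 and f = 57% when a = 0.961.

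**The case against.** The strongest objection is to the reading itself. Criterion (ii) gives SOC TCD a sensitivity of its own, which would be 100% by definition if SOC TCD were truth. The wording also parallels criterion (i), where two tests are compared and the comparator is not truth. Against a common reference such as TEE, a perfect device has sensitivity 100% and passes. This stands in part: section 11.5 does not say that SOC TCD is the reference. But section 11.2 offers no other analysis, and the common-reference reading has no defined subset, sample size or test. It also leaves open whether 90% is an absolute value or a ratio to SOC TCD.

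Three further points stand and limit the size of the problem:

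- **Prevalence.** Section 11.6 gives 30% as a floor, and above about 42% a perfect device is expected to clear 90%. Section 5.1 continues enrolment to fill ICC grades and SOC TCD is optional, so prevalence among subjects with both exams is unknown.
- **Shared errors.** Both exams are TCD, section 6.12.3 prefers one session with the same person giving the injections, and section 11.4 has a core laboratory assess both. Independent errors are therefore the least plausible case.
- **Imperfect TEE.** Section 2.3 puts TEE at 95% sensitivity and 95% specificity, so some TCD false positives may be shunts that TEE missed.

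The comparison is also secondary and unpowered. The primary endpoint and its sizing concern TTE.

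**Conclusion.** The point holds conditionally. The firm defect is that a success criterion stated as a sensitivity has no named reference, and its only specified analysis uses a comparator that the protocol itself reports as imperfect. On that analysis, the expected score at the 30% planning prevalence is 84.4% for a device in perfect agreement with TEE. It is about 82% to 100% for a device of equal accuracy. The latter range straddles the 90% target, and the position within it is set by error sharing, not by accuracy.

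A reader might infer that 84% is a ceiling for NB-IS, or that an accurate device must fail. The documents do not support either. Shared errors can lift agreement above 90%, prevalence may exceed 42%, and section 11.5 leaves the reference open.

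The figures rest on section 2.3's TCD accuracy, itself measured against an imperfect TEE, applying to SOC TCD in this trial.

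**What to change.** 1. In section 11.5 and the synopsis, stop calling the SOC TCD comparison sensitivity. State it as positive percent agreement with SOC TCD, reported together with negative percent agreement, each with a 95% CI. This matches the endpoint in section 4.2. The pair is needed because a device that calls everyone positive would have 100% positive agreement and 0% negative agreement.
2. Make the same change to the SOC TCD item in section 11.2, replacing the four accuracy terms.
3. Reserve any sensitivity statement for subjects with NB-IS, SOC TCD and TEE. Compare the two TCD methods pairwise against TEE, with a CI for the difference.
4. List the NB-IS/SOC TCD discordant pairs with their TEE result where TEE was done.

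A ratio of detection rates (NB-IS over SOC TCD) of at least 0.90 may look like a simple substitute, but it should not be used. On the same inputs a perfect device scores 0.300/0.3415 = 0.88 and fails. A device with 80% sensitivity and 80% specificity is positive in 0.24 + 0.14 = 38% of subjects, scores 0.38/0.3415 = 1.11, and passes.

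The cost is wording and a small extra tabulation of data already planned for collection. The trial gives up a sensitivity claim against SOC TCD. The three-test subset may also be small, because SOC TCD and TEE are collected only if performed. By section 11.6's own calculation, a 95% CI 20 points wide for one sensitivity already takes 147 subjects, so a smaller subset would give a wider interval.
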